We previously studied the reliability of a commercially available Dexcom G6 CGM (Dexcom, Inc., San Diego, CA) under hyperbaric oxygen conditions in healthy volunteers who did not have diabetes. This showed an increase of 3.76 mg/dL (3.72%, p<0.001) while patients were breathing HBO₂ at 2.4 atmospheres absolute (ATA) and an increase of 4.12 mg/dL (4.13%, p=0.015) when comparing pre-HBO₂ and post-HBO₂ values. The increase in EGV may have been related to increases in interstitial fluid temperature related to the HBO₂, but that was not measured. While this was statistically significant, it was not felt to be clinically relevant. The Dexcom G6 CGM was felt to be accurate and reliable for use with patients without DM receiving HBO₂. The goal for this proposed study is to look at multiple CGMs in patients with DM receiving HBO₂.

Research Goals

Specific Aim 1 – Determine whether the Dexcom G6 CGM accurately estimates blood glucose under hyperbaric oxygen conditions

Specific Aim 2 – Determine whether a single HBO₂ treatment affects blood glucose in patients with diabetes mellitus

Specific Aim 3 – Determine whether glucagon varies in relationship with HBO₂

Materials and Methods

Study Design and Timeline

This will be a prospective, controlled trial comparing a standard HBO₂ treatment vs. a control period. Each patient will serve as their own control.

December 4, 2019

Recruitment

We will recruit individuals who are living with type 1 or type 2 diabetes and are willing to undergo a single hyperbaric exposure to 2.4 ATA while breathing 100% oxygen. Participants will provide their informed consent after the risks of the study have been explained to them (*e.g.*, HBO₂ possibly decreasing BG) and the risks of HBO₂ (*e.g.*, barotrauma, confinement anxiety, oxygen toxicity, and fire). Upon enrollment in to the study, participants will have a commercial G6 CGM inserted in the subcutaneous tissue of their abdomen and a research G6 data logger inserted in the subcutaneous tissue on the back of the arm. Participants will return >36 hours after insertion for their study exposures.

Compensation up to \$400 will be pro-rated to encourage completion of all study sessions (Figure 1):

- Implantation of CGM loggers - \$50
- Completion of control study session - \$50
- Completion of HBO₂ study sessions- \$100
- Completion of follow-up data collection - \$200

Figure 1. Study Timeline and Compensation Schedule

Day		Day 1	36 hour interval	Day 3	Day 4	Day 5-9	Day 10

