- Willing to come to the hyperbaric facility on successive days (one control session and one hyperbaric treatment), spending approximately 3 hours in the facility on each day of testing
- Willing to undergo multiple fingersticks on the days of testing
- Willing to have a peripheral intravenous catheter placed for blood sampling
- Willing to perform four daily fingerstick blood glucose checks throughout the study period

Exclusion Criteria

- Contraindication to HBO₂ as determined by the study investigator (*e.g.*, pregnancy)
- Previous treatment with HBO₂ within 30 days of enrollment

December 4, 2019

- Current use of CGM is not an exclusion, but participants must use study equipment during the study
- Current use of an insulin pump
- Known allergy to medical-grade adhesives
- Extensive skin changes/disease that preclude wearing the sensor on normal skin (e.g. extensive psoriasis, recent burns or severe sunburn, extensive eczema, extensive scarring, extensive tattoos, dermatitis herpetiformis)

Control Protocol (Figure 3)

Because the effects of HBO₂ may extend longer than one day, participants will first be exposed to a 2-hour control period where they will simulate an HBO₂ exposure. Patients must be NPO after midnight of the day prior to the control study period. Participants in a control session will sit quietly (as they would in the hyperbaric chamber) and will not be allowed to consume carbohydrates unless directed to by the hyperbaric department hypoglycemia protocol. The timing of the blood draws (Figure 5) will be parallel to that of the HBO₂ exposure.

[figure not shown]
Figure 3. Control Testing Protocol

Hyperbaric Oxygen Therapy (Figure 4)

The day after the control study period, participants will undergo a standard HBO₂ treatment breathing 100% oxygen at 2.4 ATA with 3 x 30 min O₂ periods and 5 min air-breaks between O₂ periods. Patients must be NPO after midnight of the day prior to the HBO₂ period. Participants will not be allowed to consume carbohydrates during the treatment unless directed to by the hyperbaric department hypoglycemia protocol.

Figure 4. HBO₂ Testing Protocol

Modification of hypoglycemia medication regimen

Because participants are being asked to remain NPO after midnight, they will be asked to modify their normal hypoglycemic medications as follows:

- Oral hypoglycemic medications should be held until after they eat their first meal of the day

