We will use both a commercial Dexcom G6™ (Dexcom, Inc., San Diego, CA) CGM and a CGM logger for continuous glucose monitoring. A CGM logger differs from a commercially available CGM in that it does not provide feedback to the patient, but it records data that a commercially available CGM does not (*e.g.*, interstitial fluid temperature). Data can be retrieved from the logger at the end of the study period for

December 4, 2019

analysis. The G6 CGM will be inserted in the subcutaneous tissue of the abdomen according to the manufacturer's directions. The G6 CGM logger will be inserted in the subcutaneous tissue on the back of the arm according to the manufacturer's directions. We will allow at least 48 hours of runtime before hyperbaric exposure in order to allow equilibration of CGM readings. The CGM will be considered the primary data source for EGV, with the CGM logger providing a backup in case of data loss.

Home glucose monitoring

In order to verify that the CGM is working before and after HBO₂ exposure, we will have participants obtain fingerstick BG using a POC Contour One glucometer and test strips (Ascensia Diabetes Care, Parsippany, NJ) that will be provided to them. This will be done a minimum of 4 times a day throughout the study period. Data from the POC glucometer will be downloaded at the end of the study period for comparison with the CGM data.

Ancillary Data collection

We will provide all participants a log to document the time of their meals and the time of any medications taken throughout the study period.

Risks of hyperbaric oxygen (HBO₂) therapy

HBO₂ is an FDA approved treatment modality for many different conditions. It is administered in a rigid-hulled hyperbaric chamber that either accommodates a single patient (monoplace chamber) or multiple patients (multiplace chamber). Monoplace chambers are compressed with 100% oxygen while patients breathe the ambient atmosphere. Multiplace chambers are compressed with air (21% oxygen) while patients breathe 100% oxygen from a face mask or an oxygen hood. Treatment pressures range from 2.0 atmospheres absolute (ATA) to 2.5 ATA and include at least 90 minutes of oxygen breathing. Treatment protocols include periods of air breathing (air breaks) of 5-10 minutes duration interspersed between 30-minute oxygen breathing periods. The treatments start by increasing pressure during the compression phase of the treatment,

December 4, 2019

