- Use of CGM devices does not present a potential for serious risk to the health, safety or welfare of a subject.

There is a very low risk of developing a local skin infection at the site of the sensor placement and a very low risk of sensor breakage. The participant will be instructed to notify study staff if they develop swelling, redness, or pain at the sensor insertion site.

Adverse Events

We will catalog adverse events associated with HBO₂ (e.g., otic/sinus barotrauma, O₂ toxicity, confinement anxiety) or severe hypoglycemia (BG < 70 mg/dL) associated with HBO₂. We will report any complications related to the insertion of the CGM or fingersticks related to home glucose testing. Asymptomatic patients with a BG <100

December 4, 2019

mg/dL will not be considered an adverse outcome associated with HBO₂ but will be counted for analysis.

Analysis

Endpoint 1

In order to determine the accuracy of the G6 CGM in patients with diabetes who are receiving HBO₂, we will compare CGM values to laboratory results in the pre-HBO₂ NBAir (1-3), HBO₂ (4-9), and post-HBO₂ NBAir (10-12) phases. We will compare the mean absolute relative difference (MARD), which is listed at 9.9% in the Dexcom G6 user guide and has a standard deviation of 7.99 mg/dL. If we are trying to detect a difference of 5 percentage points in MARD (9.9% in room air up to 14.9% in HBO₂) with a standard deviation of 8 mg/dL, alpha level ($p < 0.05$), and a power of 0.80, we will require a minimum sample size of 18 patients.

Endpoint 2

We will compare CGM and venous blood glucose readings before (1-3), and after (10-12) each study session and use this to determine if there is any effect of session type (HBO₂ vs control) on BG. Each individual will serve as their own control, which will improve the study's power. We will determine if the BG changes observed during HBO₂ sessions are greater than those observed when the participants are sitting quietly outside the chamber during the control sessions. Linear mixed effects regression (LMER) analyses will be used to account for the clustering of data within an individual while also allowing for the main effect (difference in pre- vs. post- by session type) to be determined.

Endpoint 3

We will evaluate whether a single HBO₂ treatment affects glucagon levels by comparing control glucagon levels with the pre-, intra-, and post-HBO₂ glucagon levels.

December 4, 2019

Estimated time to conduct study

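### The Endpoint 1 sample size sets a percentage-point MARD difference against an SD in mg/dL, so the minimum of 18 cannot be verified, and at a paired SD of 8 points it holds only for an undeclared one-sided test

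*Combined protocol and SAP*

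**What the plan says.** The only sample-size calculation is in the Analysis section, under Endpoint 1.

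- **Comparison.** "we will compare CGM values to laboratory results in the pre-HBO₂ NBAir (1-3), HBO₂ (4-9), and post-HBO₂ NBAir (10-12) phases". This lists two room-air phases, one before and one after HBO₂.
- **Source of the SD.** The MARD is one "which is listed at 9.9% in the Dexcom G6 user guide and has a standard deviation of 7.99 mg/dL".
- **Effect.** "If we are trying to detect a difference of 5 percentage points in MARD (9.9% in room air up to 14.9% in HBO₂".
- **SD used.** "with a standard deviation of 8 mg/dL".
- **Result.** With alpha at 0.05, "and a power of 0.80, we will require a minimum sample size of 18 patients".

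Elsewhere, Study Design and Timeline says "Each patient will serve as their own control". Control Protocol adds a room-air day on the same sampling schedule: "The timing of the blood draws (Figure 5) will be parallel to that of the HBO₂ exposure". Recruitment plans for 24 participants, half with each type of diabetes, and states no dropout allowance.

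The Endpoint 1 paragraph does not name a test or its sidedness. It does not say whether 8 is the SD of a within-patient difference, of each phase or of single readings. It also does not say which room-air readings HBO₂ is compared with.

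**The concern.** MARD is a percentage, and the target difference is in percentage points. An SD in mg/dL cannot be divided into it without a glucose level to convert by, and the plan gives none. The mg/dL label appears twice, on 7.99 and on the rounded 8, so the intended unit cannot be taken for granted.

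The reader therefore cannot tell how many evaluable patients support the 80% power statement. If the test is two-sided, as many readers would assume where none is declared, and 8 is a paired SD in points, 18 patients fall short of 80% power. Most of the apparent reserve between 18 and 24 then disappears.

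**Working it through.** **Inputs from the plan:** difference 14.9 − 9.9 = 5 percentage points; SD 8 (from 7.99), labelled mg/dL; alpha 0.05, sidedness not given; power 0.80; planned recruitment 24.

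**Assumption needed to proceed:** 8 is read as percentage points and as the SD of the within-patient difference. The plan states neither.

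**Formula.** Paired (one-sample) t-test with n − 1 degrees of freedom and noncentrality (5/SD)·√n. Power comes from the exact noncentral t distribution. At SD 8 the standardised effect is 5/8 = 0.625.

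**Step 1: reproduce the plan's figure.** At n = 18 the noncentrality is 0.625 × √18 = 2.65.

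| n | One-sided 5% power | Two-sided 5% power |
|---|---|---|
| 17 | 79.4% | not needed |
| 18 | 81.6% | 70.5% |
| 22 | not needed | 79.8% |
| 23 | not needed | 81.7% |
| 24 | 90.7% | 83.4% |

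The one-sided minimum is exactly 18 and the two-sided minimum is 23. Using 7.99 instead of 8 changes neither. A normal approximation, (8 × (z for alpha + z for power)/5)², gives 15.8, so 16, one-sided and 20.1, so 21, two-sided. Treating the phases as independent groups gives 32 (one-sided) or 41 (two-sided) per group. Of these variants, only the one-sided paired t-test gives exactly 18. Testing the HBO₂-phase MARD against a fixed 9.9%, with a between-patient SD of 8 points, uses the same formula and gives the same numbers.

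**Step 2: vary the SD of the paired difference** (all values are assumptions).

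| Paired SD, points | 6 | 7 | 8 | 9 | 10 |
|---|---|---|---|---|---|
| Two-sided minimum n | 14 | 18 | 23 | 28 | 34 |
| One-sided minimum n | 11 | 14 | 18 | 22 | 27 |

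At n = 24, two-sided power is 83.4% at SD 8, 74.1% at SD 9 and 65.0% at SD 10.

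**Step 3: other readings of the 8** (two-sided).

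- *SD of each phase, in points.* The SD of the difference is 8·√(2(1 − ρ)). The minimum n is 43 at ρ = 0, 23 at ρ = 0.5, 18 at ρ = 0.61 and 13 at ρ = 0.75.
- *Truly mg/dL.* Converted at an assumed mean glucose of 100, 115, 150 or 180 mg/dL, 8 mg/dL is 8.0, 7.0, 5.3 or 4.4 points. Taken as a paired SD, these need 23, 18, 12 or 9 patients.

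**Step 4: reserve within the planned 24.** At a paired SD of 8 points it is 24 − 18 = 6 one-sided and 24 − 23 = 1 two-sided.

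**The case against.** The best reply is that this is a labelling slip and not a miscalculation. Once mg/dL is read as percentage points, a one-sided paired t-test returns exactly 18. The paragraph words the alternative as a rise from 9.9% to 14.9%, and the design is within-patient. The plan recruits 24, which exceeds 80% power even two-sided at SD 8, and nothing makes 18 a stopping or adequacy rule.

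Much of this stands. A reader might infer that 18 is an arithmetic error that no test can produce, but Step 1 shows that it is recoverable. The directional wording makes a one-sided test plausible. It does not declare one, because a direction for the alternative can be given for a two-sided test as well. The reply also has to supply three things that the plan leaves out: the unit, the meaning of the SD and the sidedness.

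The backup sensor is a partial answer to the thin reserve: "The CGM will be considered the primary data source for EGV, with the CGM logger providing a backup in case of data loss". It can cover lost readings from the primary sensor, but not a missed session or missing laboratory reference values.

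**Conclusion.** The point holds as a unit error and a set of unstated assumptions in the plan's only sample-size calculation. As written, the standardised effect is undefined and the 18 cannot be verified. With 8 taken as percentage points of the within-patient difference, 18 is right for a one-sided 5% paired t-test. For a two-sided test it is five patients short (23 − 18) and has 70.5% power.

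Two stronger conclusions are tempting, and the documents support neither:

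- *That the trial is too small.* At a paired SD of 8 points, the planned 24 have 83.4% two-sided power.
- *That 23 is the correct minimum.* It depends on an SD with no established unit. A paired SD of 7 points, a per-phase SD of 8 with correlation 0.61, or 8 mg/dL at a mean glucose of about 115 mg/dL each give a two-sided 18.

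This should be fixed, but it does not call the planned recruitment into question.

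**What to change.** In the Endpoint 1 paragraph:

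1. Give the SD in percentage points with its source, and say whether it is the SD of the within-patient difference or of each phase. If it is per phase, add the assumed correlation.
2. State the test and its sidedness.
3. Name the room-air comparator for the sizing (time points 1-3, time points 10-12 or the control day), and keep the post-HBO₂ comparison that the paragraph already lists.
4. Restate the minimum to match:
   - If two-sided with a paired SD of 8 points, replace 18 with 23 evaluable patients and state that the planned 24 give 83% power.
   - If one-sided, declare and justify it before data are seen, and keep 18 (82% power).
5. If the SD has no source, label it an assumption and print the two-sided minimum for paired SDs of 6 to 10 points: 14, 18, 23, 28 and 34.

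The cost is a rewritten paragraph and a search for a paired SD. No visit or recruitment target has to change. The downside is a less comfortable figure: on the two-sided reading at SD 8 the reserve falls from six patients to one. If the sourced SD proves to be 9 or 10 points, the plan would have to report about 74% or 65% two-sided power at 24.

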We will obtain a single Hba1c measurement using the central laboratory chemistry analyzer (AU680 Chemical Chemistry Analyzer, Beckman Coulter, Inc., Brea, CA) at the first blood draw to establish baseline control of their DM.

Blood glucose (central laboratory)

We will use the central laboratory chemistry analyzer (AU680 Chemical Chemistry Analyzer, Beckman Coulter, Inc., Brea, CA) to measure blood glucose at each of the time points (Figure 4). This analyzer uses a hexokinase reaction that is insensitive to blood oxygen levels and will serve as the reference for CGM and POC glucometers.

Glucagon (send-out to OHSU)

We will draw blood glucagon before (Timepoint 1), during (Timepoint 9), and after (Timepoint 12) actual or simulated HBO₂ (Figures 2-4) in order to determine whether there are any effects of HBO₂ on glucagon. The protocol for the glucagon handling is described below.

Blood sampling schedule (Figure 4)

We will obtain a venous blood glucose sample on all participants at the following time points during the study (± 2 min):

1. 30 minutes prior to starting (NBAir)
2. 15 minutes prior to starting (NBAir)
3. Immediately prior to study session (NBAir)

10-minute compression

4. 15 minutes into O₂ period 1 (HBO₂)
5. 30 minutes into O₂ period 1 (HBO₂)
6. 15 minutes into O₂ period 2 (HBO₂)
7. 30 minutes into O₂ period 2 (HBO₂)
8. 15 minutes into O₂ period 3 (HBO₂)
9. 30 minutes into O₂ period 3 (HBO₂)

5-minute decompression

10. Immediately after reaching 1 ATA (NBAir Post-HBO₂)
11. 15 minutes after reaching 1 ATA (NBAir Post-HBO₂)
12. 30 minutes after reaching 1 ATA (NBAir Post-HBO₂)

Figure 4. Timeline of testing

	Pre-HBO ₂			HBO ₂						Post-HBO ₂		
Control/HBO ₂	1	2	3	4	5	6	7	8	9	10	11	12
Time \pm 2min	T-30	T-15	T0	T+25	T+40	T+60	T+75	T+95	T+110	T+115	T+130	T+145
CGM EGV	•	•	•	•	•	•	•	•	•	•	•	•
CGL EGV	•	•	•	•	•	•	•	•	•	•	•	•
Interstitial T ⁺	•	•	•	•	•	•	•	•	•	•	•	•
Lab Glucose	•	•	•	•	•	•	•	•	•	•	•	•
NovaStat	•	•	•	•	•	•	•	•	•	•	•	•
AccuChek	•	•	•	•	•	•	•	•	•	•	•	•
TCOM	•	•	•	•	•	•	•	•	•	•	•	•
Glucagon	•							•				•

December 4, 2019

Because we are using a saline-locked peripheral IV with a 4-way stopcock for blood sampling, our protocol for each blood draw will be as follows:

- Draw approximately 4 ml of venous blood from distal port of the IV catheter, leaving the syringe in place;
- Withdraw 2 ml of venous blood and place in purple top for measurement of glucagon;

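### Endpoint 2 tests only pre-versus-post glucose, so a fall during the session that recovers or is treated before T+115 is missed, attenuated or reversed in the estimate

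*Combined protocol and SAP*

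**What the plan says.** Specific Aim 2 is to "Determine whether a single HBO₂ treatment affects blood glucose in patients with diabetes mellitus". Endpoint 2 serves that aim and names its data: "We will compare CGM and venous blood glucose readings before (1-3), and after (10-12) each study session". Its linear mixed model is meant to allow the "main effect (difference in pre- vs. post- by session type) to be determined". Between those two statements, the same paragraph puts the question more loosely: "We will determine if the BG changes observed during HBO₂ sessions are greater than those observed when the participants are sitting quietly outside the chamber".

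The Blood sampling schedule gives venous glucose at 12 timepoints, six of them (4-9) during the oxygen periods. The Control Protocol makes the control-day draws parallel to the HBO₂ day. In the Analysis section, glucose at timepoints 4-9 appears only under Endpoint 1, CGM accuracy: "we will compare CGM values to laboratory results in the pre-HBO₂ NBAir (1-3), HBO₂ (4-9), and post-HBO₂ NBAir (10-12) phases".

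The section on modifying the department's glucose protocol provides 15 g of carbohydrate when glucose is 70 mg/dL or lower before or during a study period. Endpoint 2 does not say how readings after carbohydrate are handled.

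**The concern.** The stated contrast contains no reading between T0 and T+115, which is the whole exposure. The plan nevertheless collects reference-laboratory glucose in that interval on both days, so a matched in-session comparison of HBO₂ with control is available but not assigned to Aim 2. Endpoint 3, by contrast, does use an intra-HBO₂ sample for glucagon.

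Two things are at stake. First, a real but transient effect on glucose could be reported as no effect. Second, treatment of low glucose acts on the outcome. A participant who falls, receives carbohydrate and recovers may show a normal or raised post reading, so the estimate can shrink or change sign for those who fell furthest. If an in-session window is chosen only after the data are seen, the result will carry less weight.

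**Working it through.** **Inputs.** Timepoints and phases are from the Blood sampling schedule and its timeline table; the Endpoint 2 contrast is from the Analysis section. The plan gives no effect size, variance or power for Endpoint 2. Its only sample-size figure, 18, belongs to Endpoint 1 and has no bearing here.

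**Step 1: reproduce the schedule.** With 10 min compression, three 30 min oxygen periods, two 5 min air breaks and 5 min decompression:
- Period 1 starts at 10: samples at 25 and 40.
- Period 2 starts at 40 + 5 = 45: samples at 60 and 75.
- Period 3 starts at 75 + 5 = 80: samples at 95 and 110.
- 1 ATA is reached at 110 + 5 = 115: samples at 115, 130 and 145.

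With T-30, T-15 and T0, all 12 times match the plan's table.

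**Step 2: write out the estimand.** Let d(t) be the expected HBO₂-minus-control glucose difference at time t. Then

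- post-minus-pre = mean of d(115), d(130), d(145) minus mean of d(-30), d(-15), d(0);
- during-minus-pre = mean of d(25), d(40), d(60), d(75), d(95), d(110) minus the same pre mean.

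The first expression contains no d(t) for 0 < t < 115. A fall confined to that interval contributes exactly zero, whatever its depth or shape.

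**Step 3: illustrate the size.** Depth (30 mg/dL), shape (straight lines) and timing are assumptions; the documents give none. The +15 overshoot is also assumed and is not derived from the 15 g carbohydrate dose. Pre values are set to 0.

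| Assumed course of d(t) | Values at timepoints 4-9 | Post-minus-pre | During-minus-pre |
|---|---|---|---|
| Lowest at T+60, full recovery by T+115 | -12.5, -20.0, -30.0, -21.8, -10.9, -2.7 | 0.0 | -16.3 |
| Lowest at T+60, half recovery | -12.5, -20.0, -30.0, -25.9, -20.5, -16.4 | -15.0 | -20.9 |
| Lowest at T+60, carbohydrate, overshoot to +15 | -12.5, -20.0, -30.0, -17.7, -1.4, +10.9 | +15.0 | -11.8 |
| Steady fall to -30 at T+110, then held | -6.8, -10.9, -16.4, -20.5, -25.9, -30.0 | -30.0 | -18.4 |

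First row as an example: the six values sum to about -98.0, and -98.0 / 6 = -16.3.

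**Step 4: compare sensitivity for the sustained fall.** The signal ratio, during to post, is 18.4 / 30.0 = 0.61. If errors within a session are independent with equal variance (an assumption), the standard-error ratio is √[(1/6 + 1/3) / (1/3 + 1/3)] = 0.87. Relative sensitivity is 0.61 / 0.87 = 0.71, so pre/post is the more sensitive contrast in that case.

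**Step 5: effect of carbohydrate.** In the third row the in-session contrast is also pulled toward zero, from -16.3 to -11.8. Adding timepoints 4-9 therefore reduces the masking but does not remove it.

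**The case against.** Pre/post is a legitimate choice of estimand. The Background speaks of lowered glucose after HBO₂, participants are fasting, and a fall that builds and persists is at least as plausible as a dip that recovers. Timepoint 10 comes 5 minutes after the last in-chamber sample, so a fall present at the end of exposure is seen. All of this stands, and it is why the pre/post contrast should remain the main one.

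Four stronger readings are tempting, and the documents do not support them.
- **That falls would go unrecorded.** Glucose below 70 mg/dL associated with HBO₂ is catalogued as an adverse event, and asymptomatic readings below 100 mg/dL are to be counted. However, neither is a stated HBO₂-versus-control comparison, and a fall from a high baseline that stays above 100 mg/dL and recovers is caught by neither.
- **That Endpoint 2 contradicts Aim 2.** Aim 2 asks only whether a treatment affects glucose. The reference to changes during sessions is Endpoint 2 wording and can be read as the change across the session. It is an ambiguity.
- **That the in-session contrast is better because it averages six readings instead of three.** The smaller variance ignores effect size; Step 4 shows the reverse for a sustained fall.
- **That the six in-session assays are wasted.** They are the laboratory reference for CGM accuracy in Endpoint 1 and for the glucometer comparison.

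**Conclusion.** The point holds as a gap in the Endpoint 2 analysis, not as an error that invalidates it. By construction, a fall fully recovered by T+115 contributes nothing to the estimate; this needs no assumption. A partly recovered fall is attenuated (half of an assumed 30 mg/dL fall is lost with half recovery), and a treated fall can be masked or can change sign (+15.0 mg/dL in the illustration). These sizes depend on the assumed profile. The documents do not show that a transient fall occurs, only that the stated test could not detect one that had fully recovered. The change is worth making because it helps answer Aim 2 from data the plan already collects.

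**What to change.** In Endpoint 2:
1. Keep post-minus-pre, HBO₂ minus control, as the main contrast.
2. Fit the mixed model to venous glucose with three phases (pre 1-3, during 4-9, post 10-12) and a session-by-phase term. Report during-minus-pre, HBO₂ minus control, as a prespecified secondary result. Venous glucose is the right basis because CGM accuracy under HBO₂ is itself under test in Endpoint 1.
3. Clarify whether the phrase about changes during sessions means the change across the session or the in-session readings.
4. Report the number of sessions in which carbohydrate was given, by session type, and repeat both contrasts with readings after carbohydrate set aside. This is a sensitivity analysis only, because it removes readings selectively from those who fell.
5. Keep any lowest-value summary descriptive: the minimum of several noisy readings is biased downward, and treatment cuts it short.

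The cost is added analysis wording, one more secondary contrast and one sensitivity analysis. No extra samples, visits or participants are needed.
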